6.2.3 Summary of baseline data and flow of patients

Baseline: Baseline data will be collected by the local research delivery team from the electronic medical records, using the time that is closest to the randomisation. These data will include (i) *demography*, admission diagnosis / cause of respiratory failure, medical history including chronic comorbidities; (ii) *entry at hospital*: date and time of hospital admission, date and time of ICU admission, receipt of antibiotics, Acute Physiology and Chronic Health Evaluation II score (APACHE II) (provided either by local participating site or national registry), determinants of the Sequential Organ Failure Assessment (SOFA) score, temperature; (iii) ventilation parameters, arterial blood gas, and clinical laboratory assessments.

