2.5 Participant identification / Screening

Staff will identify potential participants in appropriate clinical areas, such as emergency departments, critical care units, acute wards, operating theatres. Potential processes for identifying patients include referrals, screening in clinical areas, or review of electronic health systems using appropriate queries. We will work with each participating site to support the development of strategies to optimise screening in their hospital.

Screening information will be entered on to a trial web application, hosted by Warwick Clinical Trials Unit (WCTU). This will capture anonymised data on the numbers of patients meeting inclusion criteria for the trial but not entered into the trial along with the reasons for non-enrolment. These data are important to understand the generalisability of the recruited patient population.

Screening of patients will involve reviewing personal identifiable information. This may be undertaken by a member of the patient's existing clinical care team, or by a member of the hospital research team, depending on local arrangements. Screening and eligibility assessment may be undertaken by any individual clinically competent to undertake that role, as determined by the principal investigator. It is anticipated that this process may be undertaken at any time of day or night, provided appropriately trained staff members are available.

Patients who need intubating, or who have been intubated within the last 24 hours prior to randomisation are eligible for the trial. Confirmation that all eligibility criteria are met will be entered on to the trial web application prior to the patient being randomised.

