6.2.2 Statistical analysis plan

Primary outcome analyses

The outcome summaries and analyses will adopt the Estimand framework (as cited by the ICH E9 (R1) addendum on Estimand and sensitivity analyses in clinical trials) [33].

Summary measure and the primary Estimand: The duration of mechanical ventilation (in days) will be summarised using median, interquartile range, mean and standard deviation. The statistical analysis for this outcome will be done using the treatment policy strategy (i.e. intention to treat). Time-to event (survival models) analysis will be used to estimate the treatment effect by summarising hazards odds ratios (and 95% confidence intervals), using both unadjusted and adjusted (for site and adjusting for e.g. age and illness severity (APACHE II)) estimates. Kaplan-Meier plots will be used to display the duration of ventilation accommodating for the censored values. Intercurrent events (ICEs) and strategies for handling ICEs: post-randomisation events that may affect the interpretation of the primary outcome will include: (a) death (ICE 1); (b) cross-over (ICE 2); (b) non-compliance (including discontinuation of treatment) (ICE 3). The ICE 1 will be analysed using a composite strategy and applying competing risk models. Fine and Gray competing risk regression will be used to assess duration of ventilation, in the presence of death[34]. Competing risk regression models address the situation when more than one mutually exclusive endpoint is possible: in this case, successful extubation or death. This analysis provides a sub-distribution hazard ratio (SHR), the magnitude of which is affected by both the time to coming off the ventilator and the probability of death. SHR assesses the association between an intervention and extubation, accounting for the existence of the alternative outcome of death. The ICE 2 and ICE 3 will be analysed using the principal stratum strategy. For the ICE 2, we will

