6.3 Subgroup analyses

The following subgroups will be considered for this study:

- Baseline APACHE
- Baseline PF ratio
- Pre-existing chronic respiratory condition prior to randomisation
- Neurological/non-neurological injury
- ICU vs other intubation location

These subgroup analyses will be performed on the Intention to Treat (ITT) strategy. The primary outcome will be used as the dependent variable and interaction with treatment and sub-group. Linear regression models will be used to assess the subgroup effect, using interaction terms. As these analyses are post-hoc analyses which are not powered for any effect size, emphasis will not be based on the statistical testing, rather than the point estimates and 99% confidence intervals.

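### Baseline values are taken nearest to randomisation without having to precede it, so post-allocation PF ratio or APACHE II can enter the subgroups and the adjusted estimate

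*Protocol*

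**What the plan says.** Protocol section 6.2.3 sets the rule: "Baseline data will be collected by the local research delivery team from the electronic medical records", "using the time that is closest to the randomisation". The data covered include:

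- the APACHE II score, "provided either by local participating site or national registry", with no scoring window given;
- "determinants of the Sequential Organ Failure Assessment (SOFA) score, temperature";
- "ventilation parameters, arterial blood gas, and clinical laboratory assessments".

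Two of these feed analyses. Section 6.2.2 plans unadjusted and adjusted estimates for the primary outcome, the latter for site and "adjusting for e.g. age and illness severity (APACHE II". Section 6.3 lists baseline APACHE and "Baseline PF ratio" as subgroups.

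The setting matters. Section 2.5 identifies patients in "emergency departments, critical care units, acute wards, operating theatres" and accepts those who still need intubating as well as those intubated in the previous 24 hours. Section 2.8.1 stratifies on intubation before randomisation, and says that allocation to the device may require a tube change. Section 2.11 confirms that staff and patients know the allocation.

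**The concern.** Nearest in time is not the same as before. A blood gas taken 30 minutes after randomisation meets the rule better than one taken 2 hours earlier. In a patient already intubated, the later sample may follow a tube change that allocation prompts only in the device arm. In a patient not yet intubated, it may follow placement of the allocated tube.

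A covariate measured after allocation can carry part of the treatment's early effect, or of the disturbance caused by a tube change. Adjusting for it can then shift the estimate. A subgroup defined by such a value sorts patients partly on something allocation may have altered, so randomisation no longer guarantees comparable arms within it. Local staff who know the allocation also extract the values, so a rule that leaves the direction open gives less protection than one that fixes it.

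**Working it through.** **Step 1. Does any other text supply the missing direction?**

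| Place | What it fixes about timing |
|---|---|
| 6.2.3 | Nearness to randomisation; no direction, no window |
| 3.1, Table 2 | Baseline data, randomisation and intervention all ticked in the Baseline column; no order set |
| 6.3, chronic respiratory condition | Explicitly before randomisation |
| 6.3, APACHE and PF ratio | Called baseline; no time limit |
| 5 and 5.1 | Refer data collection to the CoReCCT Master Protocol, which is not at hand |

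Nothing in the protocol restricts the rule, and 6.3 shows that the authors wrote the restriction where they wanted it.

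**Step 2. Where do the affected values go?** APACHE II goes to the adjusted primary estimate and a subgroup; PF ratio goes to a subgroup. SOFA components are collected but named neither as a covariate nor as a subgroup.

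**Step 3. Is the sample size affected?** The plan's figure can be reproduced from 6.1, assuming a two-sided test, as sidedness is not stated. The hazard ratio adjusted for the Weibull shape is 1.2^0.901 = 1.1785. Freedman's formula, (z₀.₉₇₅ + z₀.₉₀)² × [(HR + 1)/(HR − 1)]², gives 1565 events. Then 1565 / (1 − 0.256 − 0.03) = 1565 / 0.714 = 2192, against 2194 stated. No baseline measurement enters, so the figure stands.

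**Step 4. How often could the nearest value be a later one?** The protocol does not say. As an assumption only: if samples come at a regular interval L and randomisation falls uniformly between two of them, the later one is nearer when randomisation falls in the second half of the interval. The probability is (L/2)/L = 0.5, whatever L is. Real sampling is tied to clinical events, so the true share could be lower or higher.

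**Step 5. What could the bias be?** All inputs here are assumed. Take no true effect on log duration and a severity covariate coded so that higher is healthier, with slope −0.3 per SD and residual SD 1. Let a share q of device-arm patients have a recorded value shifted down by d SD after allocation. The adjusted treatment effect is then about −0.3 × q × d. The target effect of 6/5 days is log(1.2) = 0.182.

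| q | d | −0.3 × q × d | Simulated (1,000,000 patients) | Simulated size as share of log(1.2) |
|---|---|---|---|---|
| 0.1 | 0.1 | −0.003 | −0.0016 | 1% |
| 0.3 | 0.3 | −0.027 | −0.0271 | 15% |
| 0.5 | 0.5 | −0.075 | −0.0709 | 39% |

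The simulation's standard error is about 2/√1,000,000 = 0.002, which covers the gap in the first row. A downward shift makes the device look better; an upward shift does the reverse. With d = 0, so that late values are no different by arm, the bias is zero.

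**The case against.** The best defence is that the word baseline already means before randomisation, that Table 2 lists baseline data above randomisation, and that look-back limits and time stamps normally sit in the master protocol, CRF guidance or the statistical analysis plan. Part of this stands: the protocol permits a later value but does not prescribe one, and the master protocol may narrow the rule. But row order in a table is not a rule, and 6.2.3 is not silent. It states a selection rule, and that rule followed literally admits post-allocation values. If another document is stricter, 6.2.3 still has to be aligned with it.

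A reader might infer more than the text supports:

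- *That SOFA is affected as a covariate or subgroup.* It is only collected.
- *That registry APACHE II scores post-date randomisation in patients enrolled outside ICU.* This depends on a scoring window that the protocol does not give.
- *That about half of all baseline values are late.* This needs regular sampling and a randomisation time unrelated to it; the protocol supports neither.
- *That PF ratio is late in every patient not yet intubated.* Invasive ventilator settings can exist only after intubation, but 6.3 does not say that PF ratio must come from invasive ventilation.
- *That the main result is compromised.* The unadjusted intention-to-treat estimate is also planned and uses no baseline value. The covariates are given only as examples, and 6.3 describes the subgroups as unpowered, with no emphasis on testing.

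**Conclusion.** The point holds as a badly fixed rule. As written, 6.2.3 lets a value recorded after open-label allocation count as baseline. The analyses exposed are the PF-ratio and APACHE subgroups and the APACHE II-adjusted estimate of the primary outcome. The unadjusted comparison and the sample size are unaffected.

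The size of any bias cannot be derived from the protocol. The range of about 1% to 39% of log(1.2) rests wholly on the assumed slope, share and shift. The upper end needs half of device-arm patients displaced by 0.5 SD, and no figure in the protocol supports a shift of any size. The reason to act is that the exposure is avoidable at little cost, not that a large bias has been shown. The conclusion also assumes that the master protocol does not already limit baseline values to those before randomisation.

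**What to change.** - In 6.2.3, replace the nearest-time rule with the last value recorded at or before randomisation. State a maximum look-back, and record the date and time of each value on the CRF.
- Build the PF-ratio subgroup only from such values, and define PF ratio for patients not yet intubated. The stratification factor in 2.8.1 already identifies them.
- State the APACHE II scoring window for both sources. Use the score for adjustment or subgroups only if that window does not run past randomisation.
- Otherwise, use one pre-randomisation severity measure for all patients and keep APACHE II for description or a sensitivity analysis. Substituting SOFA in some patients only would mix two scales in one covariate. SOFA components also fall under the same loose timing sentence, so they would qualify only once that is corrected.

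The cost is a sentence or two in the protocol, time fields on the CRF, and more missing baseline gas or ventilation values, mainly in patients randomised before intubation or outside ICU. For ICU patients, section 2.10 describes hour-by-hour charting, which should make earlier values available. The change is best made early, since values stored without times would have to be extracted again from source records.

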6.3 Subgroup analyses

The following subgroups will be considered for this study:

- Baseline APACHE
- Baseline PF ratio
- Pre-existing chronic respiratory condition prior to randomisation
- Neurological/non-neurological injury
- ICU vs other intubation location

These subgroup analyses will be performed on the Intention to Treat (ITT) strategy. The primary outcome will be used as the dependent variable and interaction with treatment and sub-group. Linear regression models will be used to assess the subgroup effect, using interaction terms. As these analyses are post-hoc analyses which are not powered for any effect size, emphasis will not be based on the statistical testing, rather than the point estimates and 99% confidence intervals.

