2.3 Aims and objectives

Objectives:

- (1) Conduct an internal pilot study to confirm the feasibility of a large-scale multicentre trial.
- (2) To conduct a UK-wide multi-centre, open-label, pragmatic, individually randomised, parallel group trial and economic evaluation to determine the clinical and cost effectiveness of an advanced airways protection device versus conventional endotracheal tubes (with and without basic subglottic manual suction and standard cuff) in patients with respiratory failure requiring mechanical ventilation. The outcomes are duration of mechanical ventilation, survival, ICU, and hospital stay outcomes and health-related quality of life.
- (3) Estimate, in an integrated economic evaluation, the cost-effectiveness of an advanced airways protection device versus the conventional endotracheal tubes.

Justification of outcomes

We have worked with patients, the public, researchers and clinicians to determine both our primary and secondary outcomes. This clinical effectiveness trial comprises key core outcomes from the Core Outcomes in Ventilation Trials (COVent) core outcome set and NICE guidelines for ventilation trials and NICE guidelines [5, 12, 13].

Primary effectiveness outcome

The primary variable (outcome) of interest is the duration of mechanical ventilation as measured from time from randomisation to first successful unassisted breathing, measured in days. This outcome is one of the 'COVenT' core outcomes for trials of interventions intended to modify the duration of mechanical ventilation[14]. To clarify:

- Unassisted breathing is defined as no inspiratory support or extracorporeal lung support
- Success is defined as maintaining unassisted breathing at 48 hours.
- Duration includes time receiving extracorporeal lung support, invasive mechanical ventilation and non-invasive ventilation delivering volume or pressure support ventilation.
- Duration excludes time receiving high-flow oxygen therapy and continuous positive airway pressure.
- Patients with a tracheostomy in situ may still achieve successful unassisted breathing.

Secondary outcomes - refer to CoReCCT master protocol for core clinical outcome set.

Effectiveness

- *Duration of endotracheal intubation*: time from randomisation to endotracheal extubation (in hours).
- Ventilator Associated Pneumonia (VAP): Diagnosed by treating clinician with commencement of antibiotics [16] from randomisation up to ICU discharge.

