2.8 Randomisation

2.8.1 Randomisation

A bespoke online randomisation system will be developed, by the WCTU programming team. The system will be based on a computerised algorithm using the minimisation method for randomising patients. The randomisation sequence will be created, stratified by hospital site, if the patient is intubated prior to randomisation and prior enrolment into the Awake Prone trial. Patients will be randomised, in a ratio of 1:1 to the advanced airways protection device or the standard of care endotracheal tube (with or without the basic subglottic suction/standard cuff). Randomisation can happen up to 24 hours after primary intubation. **If randomised to the intervention arm, this may necessitate a tube change. The tube change should occur within 24 hours of the patient initially being intubated.**

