6. STATISTICAL ANALYSIS

6.1 Power and sample size

We will recruit 2194 patients (1097 per arm) in total (using 90% power, 5% alpha level). Using methods based on survival analysis, the following parameters have been used for the estimation of the sample size:

- *Duration of invasive mechanical ventilation (control arm)*. Based on 133,291 admissions to 209 adult, general critical care units 1 April 2011 – 31 March 2012, the median duration of mechanical ventilation, for this trial was taken as 6 days [29].
- *Minimal clinically important difference*: In the ongoing NIHR HTA MARCH trial [30] and the BREATHE study [25], a clinically important difference of 1 day was considered to be meaningful (as defined by clinical ICU-based investigators and patient and public representatives).
- *Loss-to-follow-up*: Using the ICNARC Quarterly Quality Report Manchester Royal Infirmary, Intensive Care/High Dependency Unit (1 April 2018 to 31 March 2019) based on 2,535 patients the mortality of ventilated patients averaged at 25.6% (ICNARC, Case Mix Programme Report, 2019- obtained from ICNARC). Thus, the sample size has been inflated, to account for this loss to follow-up.
- *Withdrawal rate*: We anticipate a low rate of withdrawal of patients, as the primary outcome will be measured during the hospital stay. In our previous trials, we have consistency observed low rates of withdrawals (e.g. RECOVERY-RS 1% [24] ; BREATHE 0% [25]; HARP-2 0.5% [26]; REST 1.7% [27]). For this trial we have very conservatively assumed a withdrawal rate of 3%.
- From the above, we derive a hazard ratio of 1.2 (i.e., 6/5 days). It is anticipated that the hazards may not be constant over time (as assumed for the exponential distribution) and that the hazards are quite likely to decrease over time (as observed in the BREATHE study [31]). For this reason, the Weibull distribution may be more of an appropriate distribution, as it computes a shape parameter, p , which allows for non-constant hazards. Using the data from the BREATHE study [31], we derived the shape parameter, p , as 0.901. The hazard ratio is adjusted for this parameter and the sample size computed using the survival analysis methods.

We will review the sample size parameters with the DMC at the end of the pilot stage, using the observed data.

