use the inverse probability weighted analysis method to assess the treatment effect, having taken account of these events [35]. We will also assess the impact of crossovers on the statistical power of the study: due to the contamination effect in patients who crossover from one intervention to another, there is likely to be a reduction in the trial power. We will examine the loss of power, using power curves and different degrees of crossover, pivoted around the observed crossover rates, and assess this at the end of the pilot study as well as presenting these to the DMC at each 6-monthly analysis [36]. For ICE 3, we will use compliers average causal effect (CACE) analyses [37].

Secondary outcome analysis

In general, continuous baseline and outcome data will be summarised with descriptive statistics, including n, mean, standard deviation, median, interquartile range, and n of missing data. Mixed-effects linear regression models will be used to estimate mean treatment differences (95% CI). Categorical baseline and outcome data will be summarised with frequency counts and percentages and mixed-effects logistic regression models will be used to estimate the difference in binary outcomes between treatment groups, with odds ratios and 95% CIs reported.

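### Section 6.3 fixes linear regression for subgroup effects on a time-to-event primary outcome, gives no rule for deaths, and mislabels the analyses as post-hoc

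*Protocol*

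**What the plan says.** **Primary outcome and its model.** Section 2.3 defines the outcome as the time from randomisation to first successful unassisted breathing. Section 6.2.2 estimates the treatment effect with time-to-event models and allows for censored values. For death as an intercurrent event it names a composite strategy with competing-risk models: "Fine and Gray competing risk regression will be used to assess duration of ventilation, in the presence of death". Section 6.4 repeats that the outcome is assessed with survival methods.

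**Subgroups.** Section 6.3 lists five subgroups, makes the primary outcome the dependent variable and then fixes the model: "Linear regression models will be used to assess the subgroup effect, using interaction terms". It says nothing about deaths or censoring. It goes on: "As these analyses are post-hoc analyses which are not powered for any effect size", and it puts the weight on point estimates and 99% confidence intervals.

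**Duration of intubation.** Section 2.3 defines this secondary outcome as "time from randomisation to endotracheal extubation (in hours"). The only method in section 6.2.2 that could apply is a general one for continuous data: "Mixed-effects linear regression models will be used to estimate mean treatment differences (95% CI"). That rule names no outcome.

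**The concern.** Section 6.3 and section 6.2.2 prescribe different models for the same variable. This is text that the protocol settles, not detail left open for a statistical analysis plan. A plan that follows section 6.3 carries the mismatch forward, and one that departs from it conflicts with the protocol.

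Two things are at stake. First, a patient who dies before liberation has no observed duration. A linear model must exclude that patient, use the time to death, or assign a value, and section 6.3 chooses none of these. Second, an interaction in mean days answers a different question from an interaction in a hazard or subdistribution hazard ratio. If subgroup levels differ in typical duration or in mortality, a treatment effect that is constant on the ratio scale will look different in days. Section 6.3 asks readers to rely on the point estimates, and those are what the choice of model and of death rule moves.

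The label post-hoc is a separate matter of fact. Analyses listed in the protocol before the data are seen are pre-specified, and the wrong word would misdescribe them in the report.

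**Working it through.** **1. The plan's own figure rests on survival methods.** Section 6.1 states: "We will recruit 2194 patients (1097 per arm) in total (using 90% power, 5% alpha level"). Section 2.8.1 gives the allocation: "Patients will be randomised, in a ratio of 1:1". The other inputs from section 6.1 are a hazard ratio of 1.2, Weibull shape p = 0.901, mortality 25.6% and withdrawal 3%. Two-sided alpha is my assumption.

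- Shape-adjusted hazard ratio: 1.2^0.901 = 1.1785.
- Freedman events: (1.960 + 1.282)² × (2.1785/0.1785)² = 1565.
- Inflation: 1565/(1 − 0.256 − 0.03) = 1565/0.714 = 2192, against 2194 stated.

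The figure reproduces with deaths and withdrawals counted as patients without the event.

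**2. How many patients the missing rule could affect.** 2194 × 0.256 = 562, or 2194 × 0.97 × 0.256 = 545 after withdrawals. These are upper bounds, because section 6.1 gives mortality of ventilated patients and does not say that death came before liberation.

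**3. What a linear model on days estimates.** Assume a Weibull time to liberation with control median m and shape p. Assume also a death hazard proportional to it, with control ratio r = f/(1 − f), where f is the share dying first. Let the device multiply the liberation hazard by h and the death hazard by k. Then

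mean = m × (ln 2)^(−1/p) × Γ(1 + 1/p) × (h + rk)^(−1/p) = 1.579 × m × (h + rk)^(−1.110).

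Under proportional hazards the time of the first event is independent of its type. The same mean therefore applies whether deaths are excluded or time to death is used.

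If deaths are instead set to c days and durations are capped at c, then

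mean = πc + (1 − π) × ∫₀ᶜ exp{−(h + rk) ln 2 (t/m)^p} dt, with π = rk/(h + rk).

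**4. One common liberation hazard ratio, two subgroups.** Here h = 1.1785 and k = 1. The subgroup medians and mortality are assumed.

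- Median 3 days, 15% deaths (r = 0.1765): control 3.96, device 3.38, difference −0.57 days.
- Median 12 days, 40% deaths (r = 0.6667): control 10.75, device 9.60, difference −1.15 days.

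| Death rule | Difference, median 3 | Difference, median 12 | Apparent interaction |
|---|---|---|---|
| Excluded, or time to death used | −0.57 | −1.15 | −0.57 |
| Set to 28 days | −0.97 | −1.23 | −0.26 |
| Set to 60 days | −1.61 | −2.61 | −1.01 |

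The cause-specific liberation hazard has no interaction by construction. The linear model shows one under every rule, and its size varies about fourfold (interactions taken from unrounded values). The change of scale alone is enough to cause it. With r = 0.256/0.744 = 0.344 in both subgroups and deaths excluded, the differences are −0.44 and −1.76 days.

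**5. The sign can depend on the death rule.** This is an overall arm comparison and not an interaction. Section 6.1 gives the median: "the median duration of mechanical ventilation, for this trial was taken as 6 days". Take f = 0.256 and no effect on liberation (h = 1).

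- Death hazard × 1.25: with deaths excluded the mean moves from 6.83 to 6.37, or −0.45 days. With deaths set to 28 days the difference is +0.68, and with 60 days it is +2.06.
- Death hazard × 0.8: +0.41, −0.58 and −1.82 days respectively.
- If only half as many die first (f = 0.128, assumed), the × 1.25 case with deaths excluded gives −0.28 days.

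With k = 1 and h = 1 all of these are zero.

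**The case against.** Several points on the other side have force.

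- **Mortality.** A reader might infer that 25.6% of patients die on the ventilator. Section 6.1 does not say so. It reports mortality of ventilated patients from one unit's report, so the figure is a ceiling on the share without the event. This stands.
- **Feasibility.** A reader might infer that a linear model cannot accommodate death at all. It can, once a value is assigned under a composite strategy, and section 6.2.2 names such a strategy for the primary analysis. What remains is that section 6.3 assigns no value.
- **Duration of intubation.** A reader might infer that the protocol prescribes linear regression for this outcome. It does not. That reading comes from a general rule for continuous data, and the method for each outcome may be left to the statistical analysis plan. This stands, so the point is only a request for clarity.
- **Scale.** The clinically important difference is stated in days, and means and SDs are to be reported, so an interaction in days is interpretable in itself. That is fair. It is still not modification of the ratio that section 6.2.2 estimates.
- **Censoring.** Section 6.4 treats an absence of censoring as a reasonable assumption. It does so for the futility approximation only, and section 6.1 inflates the sample size because deaths are not expected to yield the event.
- **Harm.** The calculation with a 25% higher death hazard is hypothetical, and nothing in the protocol suggests that the device raises mortality. This stands. The calculation shows only that the unstated rule can decide the sign.
- **Importance.** The subgroup analyses are unpowered and are not meant for testing. That limits the severity but does not remove the contradiction.

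**Conclusion.** The point holds. Section 6.3 prescribes a model that does not match the primary analysis of the same outcome, and it gives no rule for deaths or censored durations. In the worked example a treatment effect that is constant on the cause-specific hazard scale appears as −0.57 against −1.15 days with deaths excluded. The apparent interaction ranges from −0.26 to −1.01 days across the death rules tried, against a stated important difference of 1 day.

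These sizes rest on assumptions: proportional Weibull hazards with the protocol's shape, illustrative subgroup medians and mortality, and illustrative death values of 28 and 60 days. They show that the problem can be material, not how large it will be in this trial. A Fine-Gray interaction need not be exactly zero in the same example, because the subdistribution hazard ratio also reflects death. The argument is for one common scale and one handling of death, not for a scale free of such effects.

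The post-hoc label is wrong as a matter of fact. A reader might infer that the trial's main result is compromised, but the documents do not support that. The primary analysis, the sample size of 2194 and the futility rule do not depend on section 6.3. Severity is should-fix.

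**What to change.** - In section 6.3, replace the linear regression with a treatment-by-subgroup interaction in the same time-to-event or competing-risk model as the primary analysis. Use the same handling of death and the same covariates, and report ratio estimates with 99% confidence intervals.
- If a difference in days is also wanted, present it as supplementary and state the value given to deaths.
- Replace post-hoc with pre-specified, exploratory.
- In section 6.2.2, state that duration of endotracheal intubation is outside the general linear-model rule and will be analysed by a time-to-event method that accounts for death. Say also how a tracheostomy that ends endotracheal intubation is counted.

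The cost is rewording two paragraphs. The first three changes need no new data, and nothing here alters the sample size or the primary analysis.
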